### **Emergency Unblinding Procedure**

Code-breaking and unblinding in the event of medical emergencies can be done by the Investigator via the IWRS, which will be accessible 24 hours per day/7 days per week.

Unblinding by the Investigator should occur only in the event of AE for which it is necessary to know the study treatment to determine an appropriate course of therapy for the subject. If the Investigator must identify the treatment assignment of an individual subject, the Investigator or qualified designee is to contact the IWRS. Unblinding performed by the IWRS at the request of the Investigator is to be reported to the Sponsor. When possible the Investigator must first discuss options with the medical monitor prior to unblinding.

Subjects for whom the code has been broken by the Investigator will be withdrawn from the study.

## **3.2. SELECTION OF STUDY POPULATION**

Up to approximately 330 subjects (i.e., 66 subjects per treatment arm) are planned to be included in the study.

### **3.2.1. INCLUSION CRITERIA**

Each potential subject must satisfy all of the following criteria to be enrolled in the study:

1. Man or woman  $\geq$  18 years and  $<$  75 years of age at the time of signing the informed consent form (ICF).
2. Diagnosis of RA (according to the 2010 EULAR/ACR classification criteria) for at least 6 months prior to screening, and ACR functional class I-III.
3. Treated with and tolerating MTX according to the following criteria:
  - a. Minimum treatment duration of 4 months prior to screening.
  - b. Stable dose of MTX of  $\geq$  12.5 mg/week to  $\leq$  25 mg/week for at least 6 consecutive weeks prior to screening.
  - c. Expected to maintain that stable dose throughout the study as described in section "Concomitant Medication".
4. Active RA as defined, for the purpose of this study, by persistent disease activity with at least 6 swollen and 6 tender joints (66/68-joint count), at the time of screening and baseline, and CRP  $>$  1.0 x upper limit of normal (ULN) at screening.
5. If using NSAIDs or other analgesics for RA, must be on a stable dose for at least 2 weeks prior to screening.
6. If using oral corticosteroids, must be on a stable dose equivalent to  $\leq$  10 mg of prednisone/day equivalent for at least 2 consecutive weeks prior to screening. If currently not using corticosteroids, must have not received oral corticosteroids for at least 2 weeks prior to first administration of study drug.
7. Chest radiograph must have been performed within 12 weeks prior to the Screening Visit or during the screening period documenting no evidence of malignancy, infection (including Histoplasmosis), or abnormalities suggestive of TB (report must be obtained and available in the subject's study file prior to baseline).
8. Subject is considered eligible according to the following TB screening criteria:
  - a. Have no history of latent or active TB on or prior to screening. An exception is made for subjects with a history of latent TB and documentation of having completed appropriate treatment for latent TB prior to the first administration of study drug. It is the responsibility of the Investigator to

verify the adequacy of previous anti-TB treatment and provide appropriate documentation.

- b. Have no signs or symptoms suggestive of active TB upon medical history and/or physical examination during screening.
- c. Have had no recent close contact with a person with active TB or, if there has been such contact, will be referred to a physician specializing in TB to undergo additional evaluation and, if warranted, receive and complete appropriate treatment.
- d. Subject should have a negative IGRA test result at screening. A subject whose initial IGRA test result is indeterminate and who has no other risk factors, radiologic findings, or physical evidence supporting latent or active TB, should have the test repeated. In case the test result is again indeterminate (or positive) the subject will be excluded from the study. An exception is made for subjects who have documentation of having completed appropriate treatment for latent TB prior to randomization and do not have other risk factors, radiologic findings, or physical evidence supporting latent or active TB.
- e. Have a chest radiograph, read by a qualified radiologist, whose diagnostic assessment is consistent with no evidence of current active TB or old inactive TB, and taken within 12 weeks prior to screening.

Note: If no chest radiograph has been performed within 12 weeks prior to screening, the assessment is to be performed during the screening period and the outcome is to be known by the time of the Baseline Visit.

9. Female subjects of childbearing potential (excluding postmenopausal women, sterilized, ovariectomized, and hysterectomized women) should have a negative pregnancy test at screening and baseline and must agree to use 2 generally accepted adequate contraceptive methods of which 1 is a barrier method (e.g., hormonal contraception stabilized for at least 1 month [oral, patch, depot, injectable, vaginal ring] in combination with condom by partner) or should agree upon continuous abstinence from heterosexual contact from screening until at least 6 months after last dosing.
- Male subjects must use condoms for the duration of the study and for at least 6 months after last administration of study drug.
10. Ability to comprehend and willingness to sign the informed consent form (ICF).
11. An understanding of and ability and willingness to adhere to the study visit schedule and other protocol requirements.

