# SCHEDULE OF ASSESSMENTS A

Study Period	Screening (Days)	Baseline (Week/ Day)	Treatment and Assessment period (Weeks)												Early Termination C (Weeks)	Follow-up D (Weeks)
			2	4	6	8	10	12	14	16	18	20	22	24		
Study Visit B	-21 to -1	0													2 (after last study drug dosing)	12 (after last study drug dosing)
Visit Number	1	2	3	4	5	6	7	8	9	10	11	12	13	14		15
Ambulatory visit	X	X	X	X	X	X	X	X	X	X	X	X	X	X	X	X
Written informed consent	X															
Demographics and medical history	X															
Physical examination	X	X							X	X		X		X	X	X
Vital signs E	X	X	X	X	X	X	X	X	X	X		X	X	X	X	X
Interferon-gamma release assay (IGRA) test	X															
Serology (hepatitis B, hepatitis C, human immunodeficiency virus [HIV])	X															
Chest radiograph F	X															
Tuberculosis (TB) evaluation (questioning) G	X	X	X	X	X	X	X	X	X	X	X	X	X	X	X	X
Review of entry criteria	X	X														
Previous medication	X															
Concomitant medication															→	
12-lead electrocardiogram (ECG) H	X															
Randomization		X														
Routine clinical laboratory analyses I	X		X		X		X									X
Extended clinical laboratory analyses (including fasting serum lipids) J		X		X		X		X		X		X	X	X	X	
Pregnancy test (serum at screening/urine at other visits) for females of childbearing potential only	X	X							X				X	X		
Interactive web response system (IWRS) notification of tender & swollen joint counts		X							X		X		X			
Study drug administration (via IWRS) K		X	X	X	X	X	X	X	X	X	X	X	X	X		

Study Period	Screening (Days)	Baseline (Week/Day)	Treatment and Assessment period (Weeks)												Early Termination C (Weeks)	Follow-up D (Weeks)	
			0	2	4	6	8	10	12	14	16	18	20	22	24		
Study VisitB	-21 to -1	0														2 (after last study drug dosing)	12 (after last study drug dosing)
Visit Number	1	2	3	4	5	6	7	8	9	10	11	12	13	14			15
Morning stiffness duration	X	X						X		X		X		X		X	X
Joint assessment (66/68-joint count)	X	X	X	X	X	X	X	X		X		X		X		X	X
Patient Pain visual analogue scale (VAS)		X	X	X	X	X	X	X		X		X		X		X	X
Health Assessment Questionnaire – Disability Index (HAQ-DI)		X	X	X	X	X	X	X		X		X		X		X	X

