#### **Pharmacokinetics**

The pharmacokinetics of ALX-0061 appear dose-dependent, suggesting target-mediated disposition of the drug. A 2-compartment disposition model with parallel first-order (linear total body clearance [CL]) and Michaelis-Menten elimination (nonlinear or concentration-dependent CL) describes well the PK behavior of the drug, and is consistent with the more than proportional increase of exposure and half-life of the drug with the increase of the dose. Similar to monoclonal antibodies, the Nanobody has a limited volume of distribution, corresponding to the plasma volume. As the PK of ALX-0061 is dose-dependent due to a different contribution of the non-linear clearance at different serum concentrations, also the terminal half-life ( $t_{1/2}$ ) is dose-dependent. At high concentrations, when non-linear clearance becomes negligible, the apparent  $t_{1/2}$  estimated from the linear clearance term only, is estimated at approximately 15 days.

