#### **3.4.1.1. ELIGIBILITY PROCEDURES**

At screening, which will take place within 21 to 1 day before the first administration of study drug, subjects will be asked to attend the clinical site to be screened according to the inclusion and exclusion criteria (section 3.2) and to have other assessments performed as specified in the [Schedule of Assessments](#).

Subjects who signed an informed consent form, but do not meet the eligibility criteria and are not randomized, will be designated a screen failure. Subjects who meet all eligibility criteria but discontinue from the study for other reasons (eg, subject request) will not be considered screen failures.

Data of all subjects screened will be collected in the (e)CRF in order to assess the numbers and characteristics of the excluded subjects, and the reasons for their exclusion.

The results from the screening procedures needed to evaluate eligibility must be available prior to the first administration of the study drug. Sites will use the central laboratory selected for the study to analyze screening samples and to use these reported values to determine eligibility.

Unscheduled visits may be planned to assess, confirm, and follow up on clinically relevant AEs or laboratory abnormalities. Findings made during these unscheduled visits should be reported in the designated sections of the (e)CRF.

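### Inclusion criterion 8c sets no deadline for the specialist evaluation of a recent close TB contact, so read literally it allows dosing while that evaluation is pending

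*Combined protocol and SAP*

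**What the plan says.** Criterion 8 in protocol section 3.2.1 has five parts, all of which must be met for enrolment. Part 8c requires no recent close contact with active TB. Failing that, it is enough that the subject "will be referred to a physician specializing in TB to undergo additional evaluation and, if warranted, receive and complete appropriate treatment". No date, visit or study event is attached to the referral, the evaluation, its result or the treatment.

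The neighbouring text is dated:

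- 8a excuses a history of latent TB given "documentation of having completed appropriate treatment for latent TB prior to the first administration of study drug".
- 8b looks for signs and symptoms during screening.
- 8d requires a negative interferon-gamma release assay (IGRA) at screening, with an exception that needs "documentation of having completed appropriate treatment for latent TB prior to randomization".
- The note to 8e says of a radiograph taken during screening that "the outcome is to be known by the time of the Baseline Visit".
- Criterion 7 adds, for the chest radiograph, "report must be obtained and available in the subject's study file prior to baseline".

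Section 3.4.1.1 has a general rule: "The results from the screening procedures needed to evaluate eligibility must be available prior to the first administration of the study drug". The Schedule of Assessments lists "Review of entry criteria" at screening and at baseline. It does not list a TB specialist evaluation.

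**The concern.** An entry criterion should be something a site can mark as met or not met on the day of dosing. As written, 8c can be marked as met once a referral is planned, whatever the specialist later finds. Sites could apply it differently, and the more permissive application is the less safe one.

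The stake is the safety of the individual subject. Section 1.2.5 acknowledges that blocking the IL-6 pathway has been reported to raise infection risk, and 8c itself treats recent contact as needing more than the standard checks. If the specialist finds TB after the first injection, the stopping rule in section 3.2.3.2 prevents further doses but cannot remove the one already given. Section 1.2.4.1 gives the apparent half-life at high concentrations, which is "estimated from the linear clearance term only, is estimated at approximately 15 days".

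**Working it through.** This is mainly a check of wording. The plan states no figure on this point, so there is none to reproduce.

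**Step 1: time points within criterion 8.**

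| Part | Subject matter | Time point |
|---|---|---|
| 8a | Treatment of past latent TB | Before first dose |
| 8b | Signs and symptoms | During screening |
| 8c | Evaluation and treatment of a recent contact | None |
| 8d | IGRA; treatment under the exception | Screening; before randomization |
| 8e and note | Chest radiograph | Up to 12 weeks before screening, or during screening with the outcome known by baseline |

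Four of the five parts are dated; 8c is the exception.

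**Step 2: does another rule supply the deadline?**

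- *Section 3.4.1.1* covers results needed to judge eligibility. On its literal wording 8c needs only the referral, so the specialist's result is not clearly one of them.
- *Sections 3.1.1 and 3.3.8* require the entry criteria to be met again at randomization. That re-applies 8c as worded.
- *8a* concerns a TB history up to screening. It does not cover an evaluation still under way, or treatment given because of contact alone.
- *8d* does not hold back a contact whose IGRA is negative.
- *Exclusion 28* allows the investigator to exclude anyone judged unsuitable. It is discretionary.
- *Schedule footnote G and section 3.2.3.2* act on suspected or diagnosed TB. Contact alone is not named as a trigger.

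None of these sets a time for the 8c evaluation or treatment.

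**Step 3: time available.** Screening takes place 21 to 1 days before the first dose (section 3.4.1.1), so the evaluation has 1 to 21 days if the contact is reported at screening. TB questioning, review of entry criteria and dosing are also all scheduled at Week 0. A contact first reported then leaves 0 days.

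**Step 4: can the other checks stand in for the evaluation?** IGRA is scheduled only at screening, so a contact occurring between screening and Week 0 comes after it. A radiograph taken before screening may be up to 12 × 7 + 21 = 84 + 21 = 105 days old at first dose; one taken during screening is at most 21 days old. Either may predate the contact.

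**Step 5: exposure if a contact is dosed.**

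- Chance of active drug: 4 of 5 arms = 80% (4 × 66 = 264 of 330 subjects).
- Drug remaining 30 days after a dose, with linear clearance only and a half-life of 15 days: 0.5^(30/15) = 0.25, or about 25%. Less remains at low concentrations, where non-linear clearance adds to elimination.

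Steps 4 and 5 are context. The finding rests on Steps 1 and 2.

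**The case against.** The best counter-argument comes from section 3.4.1.1. It says subjects are screened against section 3.2 and, separately, have the assessments in the Schedule. Criterion 8 describes its parts as TB screening criteria. On that view the specialist evaluation belongs to screening even though the Schedule omits it, and its result must be available before dosing. Moreover, 8c does not end at the referral: it goes on to evaluation and completed treatment, so a natural reading is that the criterion is met only when those are done. The amendment log also gives, as the aim of the change to criterion 8, that treatment be finished before the first dose.

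These points make the stricter reading reasonable and probably the intended one, and many investigators would likely wait. They do not put a time into 8c. The general rule applies only if the specialist's result is needed for eligibility, which is the very thing 8c leaves open. The intent in the amendment log is carried into the current wording of 8a but not of 8c.

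The objection is right about scale. An affected subject must also have no untreated TB history, no symptoms, an acceptable IGRA and a clear radiograph. TB questioning continues at later visits, and suspected TB leads to testing and to stopping the drug. Section 1.2.5 also records no serious infection with ALX-0061 so far, although that experience is small (28 and 37 subjects in the two parts of the RA study, some on placebo, and 70 healthy volunteers). The 80% and 25% figures describe allocation and elimination; they do not measure how often the problem would arise.

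**Conclusion.** The concern holds. Criterion 8c is the one part of criterion 8 without a time point, and no other rule clearly supplies one. On a literal reading, a contact who passes the other TB checks may be dosed with the additional evaluation outstanding, on the same day if the contact is first reported at Week 0.

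This assumes that at least some sites would apply 8c as written rather than as probably meant. Confidence is medium for that reason. The number of subjects affected is unknown and probably small, and the recommendation does not depend on it. Sample size, power and the ACR20 analysis are not in question. The change should be made, because the written rule permits the less safe action and the correction is simple.

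**What to change.** Amend 8c to state that, for a recent close contact, the specialist evaluation and any treatment it warrants must be completed and documented before the first administration of study drug. This is the time point 8a already uses. Sites should confirm it at the existing Week 0 review of entry criteria. Criteria 8a and 8d and the interactive web response system need no change.

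The cost is one clause, with no new visit, procedure or system item. If the change counts as a substantial amendment, section 4.1 requires ethics committee approval and, where applicable, competent authority approval. A written clarification to sites could convey the intended reading in the meantime. The downside is that a few contacts may not finish evaluation or treatment within the 21-day screening window and would become screen failures.

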### 3.2.2. EXCLUSION CRITERIA

Subjects meeting any of the following criteria may not be enrolled in the study:

1. Have inflammatory diseases other than RA, including but not limited to psoriatic arthritis, ankylosing spondylitis, SLE, sarcoidosis, or Lyme disease.
2. Presence of active infection at screening, or history of serious infection (requiring parenteral antibiotic and/or hospitalization) within 4 weeks of Baseline Visit. Minor fungal infections (for example minor fungal nail infections) will be allowed.
3. Any recurrent viral infection that based on the Investigator's clinical assessment make the subject unsuitable for the study, including recurrent/disseminated herpes zoster.
4. Have a history of, or current, congestive heart failure (CHF) class III or IV as defined by the New York Heart Association; history of unstable angina pectoris, myocardial infarction, cerebrovascular accident within 12 months before screening.
5. Have a history of demyelinating diseases such as multiple sclerosis or optic neuritis.
6. Have diverticulitis, complications of diverticulitis, a history of diverticulitis, or have symptoms potentially indicative of diverticulitis, such as gastro-intestinal hemorrhage and/or abdominal pain or unexplained change in bowel habits with fever. Diverticulosis without a history of diverticulitis or other complications is not an exclusion criterion.
7. Any history of malignancy or lymphoproliferative disease at any time, except curative treatment for non-melanoma skin cancer or resected carcinoma *in situ*.
8. Have a transplanted organ/tissue or stem cell transplantation.
9. Have a history of an infected joint prosthesis, or have received antibiotics for suspected infection of a joint prosthesis, if that prosthesis has not been removed or replaced.
10. Major surgery (including joint surgery) within 8 weeks prior to screening or planned major surgery during study or within 3 months after the subject's last visit. Hospitalization for a clinically relevant event within the 4 weeks prior to screening.
11. Have been treated with DMARDs/systemic immunosuppressives (e.g., oral or parenteral gold, sulfasalazine, azathioprine, cyclosporine, mycophenolate mofetil, hydroxychloroquine, chloroquine) other than MTX, during the 4 weeks or 12 weeks for leflunomide (except when an adequate wash-out procedure for leflunomide was completed), prior to first administration of study drug.
12. Have received intra-articular (i.a.), intramuscular (i.m.), or i.v. corticosteroids during the 4 weeks prior to screening.

13. Have received approved or investigational biological or targeted synthetic DMARD therapies for RA (including TNF  $\alpha$  inhibitors, abatacept, rituximab, or Janus kinase [JAK]-inhibitors) less than 6 months prior to screening. For subjects who received prior rituximab, subjects with an inadequate recovery of B cells should be excluded regardless of when they received rituximab.
14. Have a history of toxicity, non-tolerance, primary non-response or inadequate response to a biological therapy, or targeted synthetic DMARDs (including JAK inhibitors), for RA.
15. Have received prior therapy blocking the IL-6 pathway, such as but not limited to ALX-0061, sirukumab, sarilumab, clazakizumab, olokizumab, tocilizumab (TCZ) at any time, will be excluded.
16. Have a known hypersensitivity to the active product or any excipient of the study drug.
17. Abnormality in screening laboratory test results:
  - a. ALT and/or AST levels  $\geq$  1.5 times the ULN.
  - b. Hemoglobin levels  $\leq$  85 g/L (8.5 g/dL).
  - c. Platelet count  $\leq$   $125 \times 10^9/L$  (125,000 cells/mm $^3$ ).
  - d. White blood cell count  $\leq$   $3.5 \times 10^9/L$  (3,500 cells/ mm $^3$ ); neutrophils:  $\leq 2 \times 10^9/L$ .
  - e. Serum creatinine levels  $\geq$  1.5 mg/dL (133  $\mu$ mol/L).
  - f. Any other clinically significant abnormal screening laboratory results as evaluated by the Investigator.
18. Positive screening for hepatitis B, hepatitis C, or HIV.
19. At the discretion of the treating physician, subjects with impaired cellular or humoral immunodeficient (i.e., Ig deficiency, IgA, IgG etc.) disorders should be excluded.
20. History or presence of alcohol or drug abuse.
21. Blood donation ( $> 500$  mL) or a blood loss of comparable volume within 3 months prior to first dosing.
22. Planned donation of germ cells, blood, organs, bone marrow during the course of the study or within 6 months thereafter.
23. Male with female partner who is planning to become pregnant within 6 months of last dosing.
24. Pregnant women or female subjects who are breastfeeding.
25. History of anaphylactic reaction.
26. Administration of a live, attenuated vaccine within 3 months before dosing with ALX-0061, or anticipation that such a live attenuated vaccine will be required during the study or within 6 months after last dosing.
27. Screening 12-lead ECG that demonstrates clinically relevant abnormalities.

---

28. Subject is considered by the Investigator, for any reason, to be an unsuitable candidate for the study.

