### 3.3.6. PRIOR AND CONCOMITANT THERAPY

Prior and concomitant medication are documented throughout the study.

Prior medications as per in- and exclusion criteria are detailed in section [3.2](#).

During the screening and 24-week treatment and assessment period of the study, subjects are not allowed to initiate DMARDs other than MTX for RA (see permitted and prohibited medication below).

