#### Permitted Medication

Stable dose and route of MTX (12.5-25 mg weekly) maintained during the 6 consecutive weeks prior to screening and for the duration of the study. The concomitant medication dose may be reduced or temporarily discontinued because of abnormal laboratory values, side effects, concurrent illness, or the performance of a surgical procedure, but the change and reason for the medication should be clearly documented in the subject's medical record and in the (e)CRF.

Subjects treated with NSAIDs (including aspirin and selective cyclooxygenase 2 inhibitors) and other analgesics (except high-potency opioid analgesics, such as World Health Organization [WHO] class IV drugs [e.g., morphine; see prohibited

medication]) should receive the usual marketed doses approved in the country in which the study is being conducted and should be on a stable dose from at least 2 weeks prior to screening until the Week 24 Visit, or until the Early Termination Visit. Changes in the dose may be done at the discretion of the Investigator if the subject develops unacceptable side effects. Whenever possible, short-acting NSAIDs and other analgesics should not be administered within 6 hours before study assessments. Long-acting ones can be maintained at their usual dosing intervals before study assessments.

Subjects treated with oral corticosteroids should receive a stable dose equivalent to  $\leq 10$  mg of prednisone/day, for at least 2 consecutive weeks prior to screening, and continue this dose up to and including Week 24, or until the Early Termination Visit. The dose of oral corticosteroid may be decreased at the discretion of the Investigator only if the subject develops unacceptable side effects.

The number of intra-articular corticosteroid injections is limited to 2 injections over a 24-week period. Intra-articular injections may not be given from Week 8 until Week 12. The joint(s) affected by the procedure(s) will be considered as swollen and tender for 28 days/4 weeks in the data analyses from the date of the procedure onward.

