## Prohibited Medication

The following medications are prohibited during the study (up to and including Week 24 or Early Termination Visit):

- DMARDs other than a stable background dose of MTX.
- i.m or i.v. administration of corticosteroids for the treatment of RA. Any increase in oral corticosteroids above the baseline. For intra-articular dosing see "permitted medication".
- High-potency opioid analgesics, including but not limited to hydrocodone, metopon, oxycodone, clonitazene, hydromorphone, oxymorphone, morphine, fentanyl, levorphanol, buprenorphine, methadone, meperidine.
- Use of any biologic DMARD, targeted synthetic DMARD (such as tofacitinib), or investigational drugs.
- Use of any live attenuated vaccine.

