## 3.4.2. ASSESSMENTS OF EFFICACY

### 3.4.2.1. PHYSICIAN'S ASSESSMENT OF TENDER/PAINFUL AND SWOLLEN JOINT COUNT

To be performed as part of efficacy measurements (for more detail see sections [3.4.2.11](#) to [3.4.2.18](#)) at visits as indicated in the [Schedule of Assessments](#).

All joints listed are used in the determination of the ACR response, where 68 joints are assessed for tenderness and 66 joints are assessed for swelling (see [Appendix 9](#)). The 28 joints indicated in the grey-shaded fields are used to determine the DAS28, EULAR response, CDAI, SDAI, and Boolean score.

If tenderness or swelling is noted, enter a "1" for that joint in the appropriate field. If tenderness or swelling is absent, enter a "0" for that joint in the appropriate field.

Joints that undergo intra-articular corticosteroid injection will be considered as swollen and tender for 28 days/4 weeks in the data analyses from the date of the procedure onward.

An independent joint assessor (and backup independent joint assessor) will be designated at each study center to perform all joint assessments during the 24-weeks assessment period of the study. This individual should have at least 1 year of experience in performing joint assessments. The proposed assessors having less than 1 year of experience will need to be approved by the Sponsor. The independent joint assessor will perform only the joint assessment; this individual will not perform or assist in any other assessments in this study.

The CRO will provide training to an independent assessor from each site prior to the start of subject enrollment. In case the independent assessor cannot attend, the CRO will provide training to the Investigator who will then train the assessor. If possible, the independent assessor for the study should not be changed during the study. However, the independent assessors from each site may train additional assessors at the site for coverage during their absences. If more than 1 blinded assessor at a site performs joint assessments during the study, the names of the joint assessor performing the joint evaluation must be listed in the "Investigator Site File" and be documented in the source document at each visit.

**It is recommended that the independent joint assessor who performed the baseline joint assessments for a subject should also perform the joint assessments for that subject for all subsequent visits during the 24-week assessment period of the study.**

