### **3.6.4.1. PRIMARY EFFICACY ENDPOINT**

Under the assumption of monotonicity, a trend test will be performed as primary efficacy analysis. For small deviations from monotonicity (comprised in standard variation on ACR20 response rate), the power of the trend test remains sufficiently high. For the descriptive statistics (frequency, percentage) and trend test on the primary efficacy endpoint, data will be analyzed according to the ITT principle; thus, subjects will be analyzed according to the treatment to which they were assigned. Subjects with missing ACR20 response at Week 12 will be treated as non-responders (non-responder imputation approach).

Additionally, each dose group will be tested separately against placebo using a Chi or Fisher exact test (or other test if deemed more relevant). The study is only powered for testing the trend of the primary endpoint. All other p-values are exploratory and no correction for multiple testing is foreseen.

If ACR20 cannot be calculated at Week 12, such subjects will be considered to not have achieved an ACR20 response.

Subjects who meet any of the following treatment failure criteria will be considered nonresponder for the primary endpoint analysis:

- Initiate treatment with DMARDs (other than MTX), systemic immunosuppressives, and/or biologics for RA prior to Week 12.
- Increase dose of MTX above the baseline dose for RA prior to Week 12.
- Initiate treatment with oral corticosteroids for RA, increase the dose of oral corticosteroids for RA above the baseline dose, or receive i.v. or i.m. administration of corticosteroids for RA prior to Week 12.
- Treatment with intra-articular corticosteroids between Week 8 and Week 12.

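### No rule bars an intra-articular steroid injection between screening and first dose, so the 28-day rule can put an imputed joint into the Week 0 count used for ACR20

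*Combined protocol and SAP*

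**What the plan says.** **Before the study.** Section 3.2.2, exclusion 12, removes subjects who "Have received intra-articular (i.a.), intramuscular (i.m.), or i.v. corticosteroids during the 4 weeks prior to screening". Section 3.4.1.1 sets the interval that follows: "At screening, which will take place within 21 to 1 day before the first administration of study drug".

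**Screening period.** The one medication rule in section 3.3.6 that names this period concerns other drugs: "During the screening and 24-week treatment and assessment period of the study, subjects are not allowed to initiate DMARDs other than MTX for RA".

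**On study.** The prohibited list in section 3.3.6 covers i.m. and i.v. corticosteroids for RA. For the i.a. route it only redirects the reader ("For intra-articular dosing see") to the permitted list. That list has a cap, "The number of intra-articular corticosteroid injections is limited to 2 injections over a 24-week period", and a blackout, "Intra-articular injections may not be given from Week 8 until Week 12". Section 3.6.4.1 makes one kind of i.a. use a treatment failure: "Treatment with intra-articular corticosteroids between Week 8 and Week 12".

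**Analysis.** Section 3.4.2.1 and the permitted list both state that an injected joint is "considered as swollen and tender for 28 days/4 weeks in the data analyses from the date of the procedure onward". Neither makes an exception for baseline. Section 3.4.2.11 measures both mandatory ACR20 joint criteria relative to baseline.

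**The concern.** The plan protects the Week 12 joint count from i.a. steroids with a blackout and a failure rule, but gives no matching protection to the Week 0 count with which it is compared. The neighbouring criterion, exclusion 11, runs its washout to first study drug administration. So does inclusion 6 for subjects not taking oral steroids. Exclusion 12 includes the route that acts directly on counted joints, yet it stops at screening.

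A subject injected in the gap can enter with an imputed joint in the denominator of the primary endpoint. What is at stake is the correctness of individual ACR20 classifications, mainly in subjects with few active joints.

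**Working it through.** **1. Timing.** Inputs: injection between Day -21 and Day -1 (section 3.4.1.1); imputation for 28 days (section 3.4.2.1); Week 12 visit at Day 84 ± 3, that is Day 81 to 87 (section 3.4.1.2).
- Week 0 falls 1 to 21 days after the injection, always inside 28 days. The window ends at Day -21 + 28 = Day 7 at the earliest and Day -1 + 28 = Day 27 at the latest.
- Week 12 falls 81 + 1 = 82 to 87 + 21 = 108 days after the injection, always outside 28 days.

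So an injection in the gap is always imputed at Week 0 and never at Week 12.

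**2. Subject level.** Let r be the other joints active at Week 0 on a given count, and k the injected joints that are silent at Week 0. Inclusion 4 requires at least 6 swollen and 6 tender joints at baseline, so r is at least 6 if eligibility uses the observed count. The highest Week 12 count that still gives 20% improvement is floor(0.8 × baseline). The baseline is r as observed and r + k as imputed.

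| r | Observed baseline | Imputed, k = 1 | Imputed, k = 2 |
|---|---|---|---|
| 6 | floor(4.8) = 4 | floor(5.6) = 5 | floor(6.4) = 6 |
| 10 | floor(8.0) = 8 | floor(8.8) = 8 | floor(9.6) = 9 |
| 20 | floor(16.0) = 16 | floor(16.8) = 16 | floor(17.6) = 17 |

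For r = 6 and k = 1, a Week 12 count of 5 reads as (7 - 5)/7 = 28.6% instead of (6 - 5)/6 = 16.7%. For r = 6 and k = 2, an unchanged count of 6 reads as (8 - 6)/8 = 25%. The value k = 2 is illustrative.

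Which column is right depends on the joint before injection. If it was active on that count, the imputed baseline roughly restores the truth. If it was clear on that count (tender but not swollen, say), the imputed baseline is too lenient by the difference shown.

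**3. Trial level: the plan's figure first.** Section 3.6.8 assumes 25/30/45/55/55% with 66 per arm and a two-sided Cochran-Armitage test at 0.05, and claims power above 90%. It states no scores; equally spaced scores, centred at -2 to 2, are assumed here.
- Drift: 66 × (-0.50 - 0.30 + 0 + 0.55 + 1.10) = 56.1.
- Null variance: 0.42 × 0.58 × 66 × 10 = 160.8, root 12.68.
- Alternative variance: 66 × (4 × 0.1875 + 0.21 + 0.2475 + 4 × 0.2475) = 145.0, root 12.04.
- Power: Φ[(56.1 - 1.96 × 12.68)/12.04] = Φ(2.59) = 99.5%.

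With scores of 0/75/150/300/450 mg per 4 weeks, power is 99.1%. With 15% dropout counted as non-response it is 97.7% (equal scores) or 96.4% (dose scores). The stated figure is reproduced.

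**4. Trial level: sensitivity.** The documents give no injection frequency, so the share s of non-responders turned into responders in every arm is an assumption: p' = p + s(1 - p). The top-dose difference becomes 30 × (1 - s) points.

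| s | Difference, points | Power, equal scores, no dropout |
|---|---|---|
| 0 | 30.0 | 99.5% |
| 1% | 29.7 | 99.4% |
| 5% | 28.5 | 99.0% |
| 10% | 27.0 | 98.0% |

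These use the formula in step 3; simulation of 400,000 trials agrees to within about 0.2 points. In the harshest combination tried (s = 10%, 15% dropout by multiplying p' by 0.85, dose scores), the same formula gives 90.7%. Under the null, simulated type I error is 4.96 to 5.02%.

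**The case against.** The strongest reply is that the plan already handles an injected joint. The 28-day rule applies from the procedure onward, covers Week 0, and is the handling recommended below for anyone already injected. Distortion then needs a joint that was clear on swelling or tenderness before injection, in a subject near the entry minimum, whose Week 12 count falls exactly between the two thresholds. The subject must also meet the other joint count and three of the five further measures. All of that stands, and it keeps the point small.

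It can also be said that i.a. use during screening is permitted by design, under the cap of two. The start of the cap's 24-week period is not stated, so this reading is possible. But a cap limits the number of injections and does not bar one before Week 0. Reassessment of entry criteria at randomisation, with 6 swollen and 6 tender joints required again, controls entry but not the imputed joint. Exclusion 28 is discretionary.

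Three stronger readings are tempting, and the documents do not support them.
- **Bias between arms or a raised type I error.** The injection precedes randomisation under double blinding, so the effect is arm-neutral in expectation.
- **A steroid-suppressed Week 0 count in the analysis.** This needs the 28-day rule to be post-baseline only, and the text has no such limit. Section 3.6.2 leaves analysis details to the SAP, which could define this, but an analysis rule cannot stop an injected subject from being randomised.
- **An equal gap for i.m. and i.v. steroids.** The prohibited list bars these for RA during the study. Whether that includes screening is not stated, and use for other conditions is not covered. For these routes the text is unclear rather than plainly open.

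**Conclusion.** The point holds as a gap in the eligibility wording for i.a. injections, with a consequence that follows from the plan's own 28-day rule. At the entry minimum of 6 active joints, one injected joint that was previously clear loosens the 20% threshold by one joint, and two loosen it by two. At 10 or 20 active joints, one has no effect and two loosen it by one. There is no material threat to type I error or to the stated power of more than 90%. The power figures rest on assumed conversion rates of 1 to 10% in every arm and on assumed trend scores. This is a cheap improvement to the primary endpoint, not a defect that puts the trial's conclusion in doubt.

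**What to change.** Extend exclusion 12 so that the bar on i.a., i.m. and i.v. corticosteroids starts 4 weeks before screening and continues up to first study drug administration. This matches the endpoint of exclusion 11. Covering all three routes also removes the doubt about whether the prohibited list applies during screening.

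For any subject already injected in the gap, keep the 28-day rule as written at Week 0. Do not substitute the screening finding for that joint. Section 3.4.2.1 assigns the independent assessor to the 24-week assessment period and does not say who counts joints at screening, so a substitution could mix assessors within one baseline.

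The cost is one clause at the next amendment and a few screened subjects excluded or rescreened. Concomitant medication is already recorded from consent (section 3.4.1), so no new data are needed. Sample size, alpha and the planned test do not change.
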